1.0 Background

In July 2012, the FDA approved pre-exposure prophylaxis (PrEP) with daily tenofovir disoproxil fumarate co-formulated with emtricitabine (TDF/FTC) for reduction of sexually acquired HIV infection. Nevertheless, a major weakness of this dosing strategy is the difficulty with adherence and persistence with daily dosing. Indeed, adherence to daily oral PrEP has been so low in a number of studies as to preclude assessment of efficacy in some populations,^{1,2} and to underestimate efficacy in others.³ To date, the only real-time adherence methodology used in PrEP trials has been electronic medication containers such as MEMSCap and WisePill.^{4,5} However, these devices do not directly confirm pill ingestion, can easily be defeated by extra openings without ingestion, and data have been lost by faulty transmission or loss of devices.⁶⁻⁹ Pill counts are even more easily defeated, by pill-dumping. Although drug levels in blood have become the standard for estimating adherence, between-person variability in pharmacokinetics (PK) as well as practical and financial limits on the frequency of blood sampling prevent this approach from providing accurate day-to-day information on adherence. To accurately estimate biological efficacy in clinical trials, new methods are needed to confirm and track pill ingestion accurately over time. Software-based methods that leverage existing smartphones, do not require changes to the medication itself, and can be optimized based on participant behavior will facilitate real-time monitoring and feedback at the patient, site, and study levels. Together, these will ensure maximal adherence during trial conduct, and enable unbiased estimation of biological PrEP efficacy. Finally, an accurate and scalable adherence measurement tool that is used successfully in clinical trials has the potential to increase PrEP uptake and adherence in diverse clinical settings with high-risk populations.

In 2014, men who have sex with men (MSM) accounted for 70% of new HIV diagnoses in the United States, and MSM are the only US population in which new HIV infections are rising.¹⁰ Black and Latino men are at particularly high risk, with HIV infection rates estimated to be 6.6 and 2.9 fold higher than among White men. Disparities in HIV prevalence increased in 2008-2011, and grew fastest in the youngest age groups.¹¹ Young MSM (YMSM) accounted for nearly 20% of the estimated HIV diagnoses nationwide and over 80% of new HIV infections among youth in 2014. Furthermore, Black and Latino YMSM accounting for 55% and 33% of HIV infections among YMSM, respectively.¹⁰ Despite the promise of PrEP in preventing HIV acquisition among YMSM, PrEP uptake has been low in this vulnerable population. According to national prescription data, youth under 24 are the least likely to initiate PrEP, with only 9% of PrEP initiations in 2015 occurring in this age group.¹² In a recent national survey, only half of YMSM aged 15-24 had heard of PrEP, and 1.7% had ever used PrEP.¹³ Demonstration projects also highlight challenges with PrEP uptake and adherence. In the US Demo Project of 550 MSM, only 20% were age 25 or under, and PrEP uptake was lower among younger, non-white. and less educated persons.¹⁴ In multivariate analysis, the only independent predictors of adherence as measured by tenofovir diphosphate levels in dried blood spots were Black race (adjusted odds ratio, aOR 0.28, 95% CI 0.12-0.64) and enrollment in Miami (aOR 0.32, 95% CI 0.17-0.60).¹⁵ Self-reported adherence, pill counts, and medication possession ratios did not completely explain the disparities in TFV-DP levels. Similar findings were seen in the ATN 110 study of YMSM aged 18-22, where PrEP uptake was only 16%, and PrEP adherence was lower among Black YMSM and declined overall during follow-up, particularly with less frequent visits.¹⁶ Clearly, future PrEP studies must include sizeable numbers of African American, Latino, and young MSM, who are at high risk for HIV and may require timely adherence support, triggered by an accurate measure of adherence. Additionally, studies of on-demand (or 2-1-1) PrEP, in which 2 doses of TDF/FTC PrEP are taken in the 24 hours prior to sex, and 1 dose each taken 24 and 48 hours later, have demonstrated promise in a randomized study[refs] and

implementation programs[refs]. High adherence to this intermittent dosing regimen requires preplanning and tracking of sexual activity in relation to pill-taking.

Because of its ability to ensure treatment adherence, directly observed therapy (DOT) has been used for decades both to measure and maximize adherence for treatment of tuberculosis infection,¹⁷ and more recently has been used to ensure protocol-defined dosing in PrEP PK studies.¹⁸ A number of studies have found DOT to be successful in improving adherence to antiretroviral therapy,¹⁹⁻²¹ including in African American and Latino populations.^{22,23} However, the cost and logistical complexity of DOT in large clinical trials can be prohibitive. AiCure has developed an automated system "Automated DOT® (aDOT)" that uses artificial intelligence (computer vision and machine learning) to visually monitor adherence to treatment. Data (dosing data and patient reported outcomes) are transmitted to a centralized, cloud-based, system for analysis and intervention. On the patient side, the aDOT application is downloaded onto a smartphone and works via the front-facing camera, confirming participant identity, the medication, and correct ingestion. Visual confirmation of intentional nonadherence (confirmed fraudulent behavior) triggers alert to study staff. The platform has the potential to combine the accuracy of in-person DOT with the convenience of real-time centralized data collection and monitoring. The AiCure platform has been used in drug development and population health settings.²⁴⁻²⁶

In the DOT Diary research project (PI: [name], R01MH109320-01), the AiCure aDOT smartphone app has been adapted for use in monitoring and supporting Truvada® PrEP use among YMSM through formative work (UCSF IRB Study 15-17436) and initially piloted in the DOT Diary Cheating Protocol (IRB Study 16-18933) among 40 participants. As part of this development work, a sexual diary has been integrated into the aDOT app to assist YMSM in understanding whether they are receiving protection from PrEP for individual sexual episodes, and when it is particularly important to take PrEP (e.g. after a sexual episode). Specifically, the sexual diary allows participants to track sexual encounters, sexual behaviors that occurred in each encounter, and rating characteristics of partners. Partner-specific information (e.g. ratings) entered by participants is stored on a secure server) but is not transmitted to the study team. The app provides a calendar displaying all days in which PrEP medication was taken, and all days in which sexual activity occurred, allowing participants to see coverage of sexual encounters with PrEP. Based on pharmacokinetic and pharmacodynamic data from prior PrEP trials, the app will also indicate the estimated level of protection achieved from PrEP (e.g. low, medium, high), and also provide personalized messages on the additional numbers of doses needed to maximize protection. Additionally we have been maximizing the acceptability and ease of use of the app through an 8-week DOT Diary Optimization Pilot Protocol (IRB Study 17-22864) among 20 YMSM in San Francisco and Atlanta.

In the next stage of app development and assessment, we will conduct the DOT Diary Longitudinal Pilot to assess the impact of the app on PrEP adherence as measured by pharmacokinetic measures of PrEP use (tenofovir diphosphate [TFV-DP] and emtricitabine triphosphate [FTC-TP] levels in dried blood spots [DBS]). We will also assess the concordance of TFV-DP and FTC-TP in DBS with adherence measured by DOT Diary, and the acceptability and ease of use of the app over a longer (24-week) period. This pilot study will allow evaluation and further refinement of the app in preparation for testing in a larger efficacy trial among YMSM at risk for HIV acquisition. We will conduct this pilot protocol among YMSM in Atlanta and San Francisco Bay Area, two metropolitan regions heavily impacted by HIV,²⁷ yet differing in sociodemographics, as well as in the availability and uptake of HIV prevention services, including PrEP. These diverse research locations will allow collection of data to inform app development among a broad group of YMSM.

DOT Diary Longitudinal Pilot Protocol

2.0 Longitudinal Pilot Study Objectives

2.1 Primary Objectives

- 1. To assess the effect of DOT Diary on PrEP adherence as measured by TFV-DP in DBS among YMSM initiating PrEP
- 2. To evaluate the concordance of TFV-DP and FTC-TP in DBS with adherence measured by DOT Diary
- 3. To assess the acceptability and ease of use of DOT Diary over a 24 week period

2.2 Secondary Objectives

- 1. To assess PrEP coverage of sexual acts (prevention-effectiveness adherence) as measured by DOT Diary in the intervention arm
- 2. To evaluate the daily use of the DOT and diary components of the DOT Diary through 24 weeks of follow-up

3.0 Research Locations

The pilot study research activities will be implemented at two study sites, 1 in the Atlanta area and 1 in the San Francisco Bay area, in accordance with local approvals. These sites are the following:

- Bridge HIV, San Francisco Department of Public Health, San Francisco, California
- Emory University, Atlanta, GA

4.0 Study Population

This study is designed to enroll a diverse population of YMSM in the Atlanta and San Francisco Bay Areas. Although no restrictions are put on the racial/ethnic make-up of the study participants, sites will strive to enroll at least 50% African American or Latino YMSM into this study.

4.1 Inclusion criteria

- Self-identifies as a man
- Age 18-35 at enrollment
- Reports having insertive or receptive anal sex with a man or trans woman in the past 12 months and one or more of the following criteria in the past 12 months:
 - Any condomless anal sex outside of a mutually monogamous relationship with an HIV-negative partner
 - Two or more anal sex partners
 - Self-reported STI (gonorrhea, chlamydia, syphilis)
 - Having a known HIV-positive sexual partner
- HIV-negative as determined by a negative 4th generation HIV test at screening and negative test, per HIV testing algorithm in Study-Specific Procedures document (SSP), at enrollment.
- Willing to initiate PrEP
- Eligible to take PrEP

7

- O Creatinine clearance ≥60 ml/min as estimated by Cockcroft-Gault equation at screening
- Hepatitis B surface antigen (HBsAg) negative
- Willing and able to provide written informed consent
- Able to read and speak English
- Smartphone ownership compatible with DOT Diary app
- Meets local locator requirements
- Lives, works or plays in Atlanta Metropolitan Area, San Francisco, Alameda, Marin, Contra Costa, Santa Clara, or San Mateo Counties

4.2 Exclusion criteria

- PrEP use within the past 4 months (PrEP naïve participants will be prioritized)
- Any reactive HIV test at screening or enrollment
- Signs or symptoms of acute HIV infection at screening or enrollment
- History of pathological bone fracture not related to trauma
- Taking nephrotoxic medications
- History of participation in the active arm of an HIV vaccine trial
- In a mutually monogamous sexual relationship with an HIV-negative partner for the past 12 months
- Unable to commit to study participation for 24 weeks
- Any medical, psychiatric, or social condition or other responsibilities that, in the judgment of the investigator, would make participation in the study unsafe, complicate interpretation of study outcome data, or otherwise interfere with achieving the study objectives.

4.3 Recruitment

Participants will be recruited through a variety of strategies, including online and social media strategies (e.g. craigslist, Grindr and Facebook ads); distributing posters, flyers, and palm cards about the study; and direct outreach at local venues frequented by YMSM, including community based organizations, schools, churches, and community events. Those that express interest through advertisements will be followed-up with by study staff via phone and/or email, if preferred. In addition, former participants who have previously given consent to be contacted for future research may also be directly contacted for recruitment.

4.4 Co-enrollment Guidelines

Participants in this study will not be allowed to take part in other concurrent interventional research studies during their participation in this study; co-enrollment in observational studies may be allowable with approval of the protocol team. This is due, in part, to concerns about participant study burden, American Red Cross-mandated limitations on per-unit-time phlebotomized blood volumes, and confounding in the interpretation of the study data.

4.5 Participant Retention

Once a participant enrolls in the DOT Diary Longitudinal Pilot, the study site will make every effort to retain him for the entire follow-up period in order to minimize possible bias associated with loss-to-follow-up. Study site staff are responsible for developing and implementing standard operating procedures (SOPs) that reflect retention strategies necessary to achieve the retention goal of 90% at the final study assessment/visit. Components of such procedures may include:

- Thorough explanation of the study visit schedule and procedural requirements during the informed consent process and re-emphasis at each study visit.
- Collection of detailed locator information at the study Screening Visit and updating of this information at each subsequent visit, if necessary.
- Use of appropriate and timely visit-reminder mechanisms.
- Immediate and multifaceted follow-up for missed visits.

4.6 Participant Withdrawal

Regardless of the participant retention methods used, participants may voluntarily withdraw from the study for any reason at any time. The site investigator also may withdraw participants from the study to protect their safety and/or if they are unwilling or unable to comply with required study procedures after consultation with the Protocol Team. Participants also may be withdrawn if the study sponsor, government or regulatory authorities, or site IRBs/ECs terminate the study prior to its planned end date. Study staff will record the reason(s) for all withdrawals from the study in participants' study records.

5.0 Study Design

5.1 Overview

This is a pilot study to assess the effect of DOT diary on PrEP adherence among YMSM, and to assess the acceptability and ease of use of the DOT Diary app in this population over a 24 week period. We will enroll up to 100 total participants (approximately 50 per city) who have not been on PrEP in the last 4 months (PrEP naïve participants are preferred) and are willing to initiate PrEP at the enrollment visit. Participants will be randomized 2:1 to receive (intervention arm) or not receive (control arm) the DOT Diary app at enrollment. Participants will return for follow-up visits at 6, 12, 18, and 24 weeks for safety assessments, pharmacologic measures of adherence (tenofovir diphosphate [TFV-DP] and emtricitabine triphosphate [FTC-TP]), study drug provision, and quantitative and qualitative acceptability assessments.

5.2 DOT Diary app

DOT Diary is a smartphone app designed to track participant adherence to oral PrEP use and sexual behaviors on a day-by-day basis. DOT Diary is built upon AiCure's HIPAA-compliant platform which uses artificial intelligence (computer vision and machine learning) to visually monitor adherence to treatment. Computer vision and neural networks confirm that the correct participant is presenting the correct medication and ingesting the medication. Real-time data (dosing data and patient reported outcomes) are transmitted to a centralized, cloud-based, system for analysis and

intervention. Data are presented to study personnel on a browser-based dashboard. Study personnel may switch on automated notifications (notifications are based on adherence thresholds). Study personnel receive weekly updates regarding participants. In addition to dosing data, the platform will automatically flag behavioral events for further review that may be indicative of a participant intentionally not taking the medication, or 'feigning' adherence. If deceptive behavior is confirmed by human review, study personnel are notified. On the participant side, the aDOT application is downloaded onto a smartphone and works via the front-facing camera. Dosing data are encrypted and stored, then transmitted to centralized servers; all protected health information (PHI) is encrypted and withheld from view on the dashboard.

To facilitate participant tracking of sexual encounters, a sexual diary has been integrated with the AiCure aDOT system to create the DOT Diary app. The sexual diary allows participants to track sexual encounters, sexual behaviors that occurred in each encounter, and rating characteristics of partners. Ratings characteristics are subjective items such as physical attributes, chemistry, personality, and overall; participants can rate each characteristic on a scale of 1-5 stars. These are features that were requested by participants in earlier formative work during app development to increase usefulness and acceptability of the app. Partner-specific information (e.g. ratings) entered by participants is not shared with the study team. Participants are instructed to only use nicknames for their partners and to not include any protected health information identifiers, such as phone number, date of birth, address, email address, etc. There are no fields in the sexual diary to record this type of identifier. The app will provide a calendar displaying all days in which PrEP medication was taken, and all days in which sexual activity occurred, allowing participants to see coverage of sexual encounters with PrEP. Based on pharmacokinetic and pharmacodynamic data from prior PrEP trials, the app will also indicate the estimated level of protection achieved from PrEP (e.g. none, low, medium high), and dosing needed to maximize protection. Participants will be provided information that these are estimates of protective levels, and that protection from PrEP is not 100%. Additionally, the app will provide summary data on doses taken, sex partners, and sexual activity in graphical form to promote participant insights and reflection about their pill-taking and sexual behaviors.

Although the data entered into the sexual diary is being stored on servers through AiCure, partner-specific information is only being stored for participant data back-up purposes and will not be accessed or used by AiCure for any purpose. Information about sexual encounters (excluding partner nickname and ratings) will be used for the data visualization summaries described in the previous paragraph as well as for data analysis by the study team.

5.3 Randomization

Participants will be randomized in a 2:1 ratio to the intervention (N=67) or control (N=33) conditions, using randomly-permuted blocks of randomly selected size 3 and 6, stratified by site (San Francisco, Atlanta). The randomization scheme will be generated and archived by the study statistician, and implemented in RedCap.

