5.6.2 Enrollment visit

Participants who are eligible after screening will return to the clinic for an enrollment visit. All screening procedures must be complete within 4 weeks (28 days) of the enrollment visit. At the enrollment visit, HIV testing will be performed according to HIV testing algorithm in SSP. Participants will complete an online questionnaire via computer-assisted self-interview (CASI) that gathers data on baseline demographics, drug use and sexual behaviors, knowledge and use of PrEP, and experience using technology. Participants will also be provided risk reduction counseling, condoms, and lubricant. A study clinician will then perform a medical history and limited physical exam (this may be done at screening and updated at enrollment, based on site preference). Study staff will confirm participant eligibility and enroll the participant into the study.

Participants will then be randomized to receive the DOT Diary intervention immediately at enrollment (intervention arm) or PrEP alone (control arm) in a 2:1 ratio (see randomization procedures in Section 5.3). Participants who are randomized will be considered enrolled in the study. Participants in the intervention arm will be provided instructions to download the app on to their smartphone. Study staff will demonstrate how to use the DOT Diary app, and participants will complete the tutorial in the app and demonstrate taking their first dose of TDF/FTC using the app. Participants will also select a daily dosing time, and the app will be programmed to send the participant a daily text message or app notification at this time to take their pill and use the app. Participants will also set preferences regarding the sexual diary, including preferences regarding partner rating items. Staff will instruct participants to not include any personally identifiable information about partners in the sexual diary, such as real names or contact information. Staff will emphasize that partner nicknames should be used that help the participant identify the partner but are not easily identifiable to anyone else. For example, "Bob" or "Leather pants guy."

All participants will be dispensed 3 bottles of TDF/FTC (90 pills) and provided the PrEP Basics handout and adherence counseling regarding importance of daily adherence to PrEP for maximal protection and strategies to integrate pill-taking into one's routine. The participant will be provided a stipend for completion of the enrollment visit.

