6.2 Statistical Analysis

6.2.1 Primary Objectives

The primary objectives of the study are:

1. To assess the effect of DOT Diary on PrEP adherence as measured by TFV-DP in DBS among young MSM initiating PrEP

We will use GEE logistic models to estimate the average effect of assignment to DOT Diary on repeated TFV-DP levels ≥700 fmol/punch, which are consistent with taking 4-7 PrEP doses per week. In exploratory analyses, we will examine whether the between-group difference increases over time. We will also use analogous GEE linear models to estimate the effects of D2 on log-transformed TFV-DP levels, as well as GEE proportional odds models for an ordinal outcome defined as TFV-DP levels consistent with <2, 2-3, and 4-7 doses per week, using cut-points determined by pharmacokinetic benchmarks established through directly-observed dosing.²⁹

Minimum detectable effects (MDEs). We used data from the EPIC study to estimate the baseline level and intraclass correlation (ICC) of the repeated binary measures of DBS TFV-DP levels \geq 700 fmol/punch as 60% and 0.69 respectively, and retention of 80% of participants at 24 weeks. Under these assumptions, we will have 80% power in 2-sided tests with a type-I error rate of 5% to detect average between-group differences in adherence of 23 percentage points.

2. To evaluate the concordance of TFV-DP and FTC-TP in DBS with adherence measured by DOT Diary

Validation of DOT will focus on concordance between aDOT-based assessments of PrEP adherence by the AiCure device with four DBS measurements:

- a. We will use a pharmacokinetic (PK) model with parameters estimated in the DOT-DBS Study (NCT02022657) to calculate the expected TFV-DP levels when each DBS is obtained, based on the aDOT-based pattern of pill-taking over the previous 6 weeks. We will then estimate the correlation between these predictions and observed TFV-DP levels based on DBS, and scatterplot the two measures against each other, with a Lowess smooth. As an additional measure of concordance, we will estimate the proportion of 90% prediction intervals obtained from the PK model that include the measured DBS TFV-DP levels.

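### Section 5.3 prints the within-site block sizes (3 and 6), so site staff who see past assignments and confirm eligibility could foresee up to about 10% of assignments; the sizes should be withheld from sites

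*Protocol*

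**What the plan says.** Protocol section 5.3 (Randomization) sets the ratio and arm sizes: "Participants will be randomized in a 2:1 ratio to the intervention (N=67) or control (N=33) conditions". For the method, the same section specifies allocation "using randomly-permuted blocks of randomly selected size 3 and 6, stratified by site (San Francisco, Atlanta"). It adds: "The randomization scheme will be generated and archived by the study statistician, and implemented in RedCap". Section 5.1 sets the scale: "We will enroll up to 100 total participants (approximately 50 per city"), so each site stratum is a sequence of about 50.

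On who controls entry, section 5.6.2 (Enrollment visit) states "Study staff will confirm participant eligibility and enroll the participant into the study", and randomisation follows at the same visit. One exclusion in section 4.2 is discretionary; its grounds include any condition which, "in the judgment of the investigator, would make participation in the study unsafe, complicate interpretation of study outcome data".

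On visibility of the arm, section 5.6.2 continues: "Participants in the intervention arm will be provided instructions to download the app on to their smartphone". Staff then demonstrate the app to those participants.

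Neither the protocol nor the SAP says that block sizes are withheld from sites. Beyond the statistician's list and REDCap, no further concealment is described.

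**The concern.** Allocation is concealed only if the person deciding on entry cannot foresee the next assignment. With permuted blocks, someone who knows the possible sizes and has seen every earlier assignment in the stratum can sometimes work out what must come next. Site staff can see the history, and the protocol they work from gives the sizes.

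If the next arm can be foreseen, it can influence who is confirmed as eligible or who is scheduled for that slot. The primary outcome is adherence, which depends on the person, and the protocol's background section reports lower adherence in identifiable groups. Staff could therefore hold expectations about a candidate. The primary comparison has only 33 controls, and the primary GEE logistic model, as described in both documents, names no baseline covariates that might offset a difference at entry.

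**Working it through.** **1. The plan's own benchmark.** Protocol section 6.2.1 and the SAP state a minimum detectable difference of 23 percentage points at 80% power, two-sided 5%, with a 60% baseline level and an ICC of 0.69. Section 6.2.1 also gives a mean of 3.59 DBS per participant in the 67-person arm, which is applied here to both arms.

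- Effective n = n × 3.59 / (1 + 2.59 × 0.69) = n × 1.288.
- Control: 33 × 1.288 = 42.5. Intervention: 67 × 1.288 = 86.3.
- A pooled-variance test of two proportions, solved for 80% power, gives 23.0 points. The stated figure reproduces.

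**2. How assignments become certain.** At the start of a site's list the block holds either 2 intervention and 1 control (size 3) or 4 and 2 (size 6).

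- If the first two assignments are both control, the block must be of size 6, and the next four must be intervention.
- If the first four are all intervention, the block must again be of size 6, and the next two must be control.

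Later in the list the observer keeps a probability for each possible block state and updates it after each assignment. An assignment counts as certain when every state still possible leaves only one arm.

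**3. Predictability of the printed design.** Inputs: ratio 2:1, sizes 3 and 6, 50 assignments per site, and an observer with the full site history. The documents do not give the probability of choosing each size, so it is varied. Simulated site sequences give:

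| Probability of size 3 | Certain | of which intervention | of which control | Best guess right |
|---|---|---|---|---|
| 1/3 | 11.9% | 9.4% | 2.5% | 75% |
| 1/2 | 9.9% | 7.8% | 2.1% | 75% |
| 2/3 | 7.4% | 5.9% | 1.6% | 76% |

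With no knowledge, always guessing intervention is right 67% of the time. At equal probabilities the certain share is 0.099 × 50 = about 5 assignments per site, or about 10 of 100 overall. The probability of intervention exceeds 80% on about 35% of occasions and is below 50% on about 14%.

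**4. Comparators, with the sizes known to the observer.**

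| Block sizes | Certain | Best guess right |
|---|---|---|
| 3 only | 43% | 77% |
| 6 only | 28% | 74% |
| 3 and 6 (equal) | 9.9% | 75% |
| 6, 9 and 12 (equal) | 2.2% | 71% |

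For known sizes 6, 9 and 12, the share of occasions above 80% stays at about 34%, and the share below 50% rises to about 19%.

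**5. An illustrative size of bias (inputs assumed).** If staff steered every slot, with both a likely good and a likely poor adherer always available, the arms could differ by 0.425 in the share of likely good adherers. Suppose candidates differ by 20 points in expected adherence and staff steer on 10% to 25% of occasions. The bias is then 0.425 × 20 × 0.10 = 0.85 to 0.425 × 20 × 0.25 = 2.1 points. That is under a tenth of 23 points.

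**The case against.** The protocol already has partial safeguards. The block size varies at random, which brings certainty down from 28–43% for fixed known blocks to about 10%. The statistician generates and archives the list, REDCap holds it, and eligibility is confirmed before randomisation. The outcome is a laboratory assay. Small blocks also protect the 2:1 balance in strata of about 50, which is a legitimate choice. Most of the certain calls are intervention, already the likelier arm, and only about 2 in 100 are certain control. The 10% assumes someone who tracks every assignment exactly. Screening must be complete within 28 days of enrolment, which limits waiting for a preferred slot.

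Much of this stands, and it limits the size of the problem. It does not remove it. REDCap hides the list but not what can be deduced from printed sizes and visible history. Eligibility before randomisation is the step at which such selection would act. An assay limits measurement bias but cannot correct a difference in who entered each arm.

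Three stronger readings are tempting and are not supported:

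- *That the comparison is biased.* Nothing in the documents shows that anyone has predicted or steered assignments.
- *That the arms could differ by some 42 points in likely good adherers.* This needs steering at every slot with both kinds of candidate always to hand, which nothing in the documents suggests.
- *That larger blocks would remove most of the foreknowledge at no cost.* If 6, 9 and 12 became known, certainty would fall to about 2%. The best guess would fall only from 75% to about 71%, and maximum steering only from 0.425 to 0.329. On the assumptions in step 5, that saves (0.425 − 0.329) × 20 × 0.10 to 0.25 = about 0.2 to 0.5 points, with slightly more possible imbalance.

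**Conclusion.** The point holds as a low-severity weakness in allocation concealment. With sizes 3 and 6 printed and equally likely, at most about 10% of assignments could be known in advance (about 7% to 12% over the range of size probabilities), and the best guess improves from 67% to 75%. These figures describe a fully attentive observer with a site's complete history, so they bound the opportunity and do not measure a bias. That sites know the sizes is inferred from their working to this protocol. The 0.9 to 2.1 point illustration rests on assumed inputs and is small beside the 23-point detectable difference. The case for acting is that the opportunity is avoidable at very little cost. No stated figure in the plan is wrong on this point.

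**What to change.** In Protocol section 5.3, replace the printed sizes with: *randomly permuted blocks of varying size, stratified by site; block sizes are held by the study statistician and not disclosed to sites*. Because the current sizes are already in the protocol, the statistician should generate a new list with undisclosed sizes for participants not yet randomised and load it into REDCap.

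Larger multiples of 3 (for example 6, 9 and 12) are an optional backstop in case the sizes become known. Non-disclosure is the main remedy. If enrolment is already complete, report the block sizes and the predictability they imply, and compare baseline characteristics by arm.

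The cost is a wording change and a new REDCap list. Larger blocks, if chosen, add a slightly larger possible imbalance from one incomplete block per site. Sample size, endpoints and analysis are unaffected.
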